While there is longstanding expert agreement that LBP patients should be classified into subgroups prior to treatment,¹⁸⁻²⁰ no classification systems specific to the geriatric LBP population have been developed. There is strong evidence that classification approaches, where treatments are matched to the patient's limitations of that specific sub-group, can improve outcomes for patients undergoing physical therapy treatment for LBP.²¹⁻²⁴ To develop effective treatments, we must develop appropriate classification systems for older adults with chronic LBP.

Our preliminary data from the initial testing of the proposed hip-focused treatment among older adults with LBP suggest that this LBP subgroup may have a more favorable treatment response when the identified hip deficits, i.e. limitations, are also addressed. Therefore, the natural next step is to refine and further explore this hip-focused treatment for this newly identified at-risk subgroup (i.e. those with hip pain and weakness) through a well-controlled clinical trial. We propose a multi-site, single-blinded (i.e. examiners will not know participant treatment group assignment), randomized-controlled (i.e. participants will have an equal chance of getting 1 of 2 treatment plans), trial that advances findings from our previous study. We will recruit a total of 180 older adults with LBP of at least 3 months duration (i.e. chronic LBP) who are classified as members of the at-risk hip-spine subgroup. We will investigate whether a hip-focused treatment plan warrants further investigation as an approach to improve LBP and outcomes among older adults with chronic LBP. Manual therapy techniques will be used to address hip joint pain and progressive strengthening will be used to address hip weakness in one treatment group as compared to a LBP-focused treatment including manual therapy techniques to the low back region and low back muscle stretching. We will measure disability, LBP intensity, physical function (i.e. walking speed, chair rise performance, balance) and clinical hip deficits at baseline and after 8 weeks of intervention. We will also do a follow-up at 6 months (16 weeks post-treatment) to assess whether improvements hold from post-treatment to 4 months post-treatment.

The goals, i.e. specific aims, of the proposed research are to:

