1. Explore whether a hip-focused treatment leads to reduced disability and improved physical function when compared to a low back-focused treatment in an at-risk hip-spine subgroup (i.e. those with both hip pain and weakness, in addition to low back pain).
2. Determine what contributes to improvements in disability and physical function in this at-risk hip-spine subgroup.

6. PROCEDURES Describe all procedures involving human subjects for this protocol. Include copies of all surveys and research measures.

Study Participants.

Participants with moderately intense (LBP rated at least 4/10), chronic LBP (pain of at least 3 months) that impacts daily activities with concurrent hip pain and hip weakness will be recruited from newspaper and online advertisements, as well as from databases of former study participants who have agreed to be contacted for future studies. The sample will be recruited from one of three areas in this multi-site clinical trial: Newark, DE and surrounding communities, Pittsburgh, PA and surrounding communities and Durham, NC and surrounding communities.

Design and Randomization Plan.

In total, 180 participants meeting the inclusion/exclusion criteria will be randomly assigned into one of two intervention groups: (1) spine treatment supplemented with a hip-focused manual therapy and hip-focused exercise intervention, or (2) spine-focused rehabilitation with stationary cycling. We will use statistical software to generate a randomization plan that ensures by the end of the study that an equal number of participants are randomly assigned to each of the two treatment conditions. We will perform randomization separately in men and women given the reported sex differences in pain conditions among older adults²⁵, this approach will ensure equal randomization of men and women into both randomization groups. The treatment assignments will be uploaded into the web-based data entry application for the study. A participant's study allocation will be revealed to approved study personnel (i.e. not physical therapy testers) once all eligibility criteria have been entered and eligibility is confirmed.

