Pre-Entry Phase. Potential exclusions will be examined in two phases, first over the telephone using a structured questionnaire, then on-site with a standardized history and physical examination performed by a licensed physical therapist to validate the inclusion and exclusion criteria obtained by telephone. All of the on-site screening procedures will be performed after individuals have signed informed consent. All persons screened via phone or on-site will be assigned a number. If they are ineligible, a reason will be listed. They will also be asked if they would like to be contacted for future studies. If they verbally consent to future contact, their name, age, and contact information will be kept in a separate password protected folder under an encrypted UD server. All other documents will be shredded.

Assessments. All participants who are included based upon the screening criteria will receive identical pre-treatment assessments. A trained research assistant (masked to the intervention assignment) will administer outcome measures at baseline, prior to randomization. The same assessments will be made at the end of the intervention (i.e. 8 weeks post-enrollment) and 16 weeks post-treatment (i.e. 6 months post-enrollment).

Primary Outcome Measures

Self-Report Measures: These questionnaires evaluate self-perception:

1. **Pain-Related Disability:** The Quebec Back Pain Disability Scale²⁶, is reliable and valid questionnaire, which assesses low back pain-related disability. It has an established minimally clinically important change of 30%.²⁷
2. **Pain Severity:** Pain Thermometers (which have excellent reliability in older adults^{28,29}) will be used to assess pain severity in both the lumbar spine and hip at baseline, post-treatment, and 6 months.
3. **Patient-Reported Outcomes Measurement Information System (PROMIS)-29:**³⁰⁻³⁴ Developed by

the National Institutes of Health (NIH), the PROMIS-29 is a bank of questions for the clinical research community. It has demonstrated good reliability and construct validity for evaluating health-related quality-of-life. The PROMIS-29 profile includes questions assessing the following domains: physical function, anxiety, depression, fatigue, sleep disturbance, ability to participate in social roles and activities, pain interference, and pain intensity.

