Functional Performance Measures: Observed measures of functional performance that focus on mobility-related function will be included because observed measures and self-report measures evaluate distinct constructs. Performance will be assessed with the:

1. **10 Meter Walk Test:** This is a reliable³⁶ and valid³⁷ test that asks participants to walk along a linear pathway. The test will be conducted at the participants 'usual pace' and 'as quickly as possible, but safely' for three trials per condition. Average gait speed will be determined using the central 6 meters of the course, allowing for 2 meters of acceleration and deceleration at either end. The minimally clinically important change is .07 m/sec.³⁸

2. **Timed Get-Up-and-Go (TGUG)**³⁹⁻⁴¹: This test measures the time it takes a person to rise from a standard height chair (seat height 46 cm) with armrests, walk 3 meters, and return to a seated position in the same chair. One practice test is performed followed by three recorded trials. The test has proven to be reliable and valid for quantifying functional mobility in a variety of patient populations.

3. **Six-Minute Walk Test:** This test measures the distance that a person walks during a six minute timed period. This test has been used extensively to evaluate exercise tolerance in older adults.⁴² We will ask patients to report their low back pain intensity (0-10) before walking and at each minute of the test.

Adverse Events: The occurrence of AEs is monitored for each participant on an ongoing basis throughout the study by all study staff who interact with the participant, including during on-site assessment visits, intervention sessions and during monthly phone calls between the immediate post-intervention assessment and the final assessment at 6 months.

An adverse event (AE) will be defined as any unfavorable or untoward medical occurrence in a human study participant, including any abnormal sign (e.g., abnormal physical exam or laboratory finding), symptom, or disease, temporally associated with the participant's involvement in the research, whether or not considered related to participation in the research.

Some examples of adverse events include:

- Any new and pre-existing symptoms or conditions that have become worse either in frequency or severity or both, even if the event was not caused by the study treatment or procedure.

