- Any recurrence of previously resolved condition whether or not it is related to the study treatment or procedure.
- Any clinically significant findings from the study-related or non-study related procedures such as vital sign measurements, physical exams and any other procedures.

A serious adverse event will be considered one that:

- Results in death
- Is life threatening, or places the participant at immediate risk of death from the event as it occurred

- Requires or prolongs hospitalization
- Causes persistent or significant disability or incapacity
- Is another condition which investigators judge to represent significant hazards

After consent and prior to randomization, only adverse events that are a direct result of study procedures determined by the site principal investigator (PI) or occur while the participant is under study staff supervision will be recorded. Examples of AEs that will be tracked prior to randomization include (but not limited to): falls during the functional testing or emotional distress caused by the questionnaires. Following randomization, all AEs, regardless of relationship to study procedures, will be collected until the end of the study.

Secondary Outcome Measures

Self-Report Measures

1. Research Task Force (LBP) Impact Score⁴³: This will be used to assess the personal impact of LBP. Impact is defined as a combination of pain intensity, pain interference with normal activities and function, using 9 items from the 29-item PROMIS short form (score range: 8-50). NOTE: This questionnaire will also be used as part of inclusion/exclusion screening.
2. Low Back Activity Confidence Scale: A relatively new questionnaire that measures a person's confidence in their ability to perform 15 different activities, including carrying, pushing, sitting, walking, and exercising, that may be directly affected by low back pain. Reliability and validity has been previously established.⁴⁴

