Quebec score and gait speed will be used to test our specific hypotheses about short-term (immediately post-treatment) and longer-term (6-months post-randomization) changes in disability and pain severity. We will use linear mixed models with time (baseline, 8 weeks and 6 months) and the group*time interaction as fixed effects while controlling for repeated measures using an unstructured correlation matrix between time points. The effect of time will be treated as categorical. No main effect for treatment is included as the baseline means are assumed and constrained to be equal due to randomization. We will also control for site and sex as fixed effects since these are stratification factors in the randomization. We will use linear contrasts to test HIP+ versus SFR at 8 weeks and 6 months (Aim 1). GLMM assumptions include homoscedasticity, normality, and linearity using standard graphical methods, the Shapiro-Wilk test, and Box-Cox test respectively. If model assumptions are violated, we will consider transformations (e.g. Box-Cox method) that can be applied but maintain interpretability. We will test the secondary outcome measures related to Aim 1 in the same fashion to identify which outcomes should be considered in future trials.

The rates of individual adverse events and serious adverse events that occur >10% and adverse events classified by organ system and relatedness will be calculated for each group and compared using Chi-square or Fisher's exact tests.

Aim 2: Hypothesis. Reductions in hip joint pain, increases in hip strength and increases in functional self-efficacy will be associated with improvements in LBP-related disability and physical function.

Two sets of regression analyses will be used to determine the degree to which changes in hip pain, hip strength and functional self-efficacy explain changes in LBP-related disability and physical

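### Adverse events labelled as related are tested between arms although no masked causality review is described, so a significant result could reflect attribution rather than harm

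*Combined protocol and SAP*

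**What the plan says.** Section 10 (Data, Statistical Analysis, Aim 1) commits to rates of individual AEs and serious AEs occurring in more than 10%, and states that "adverse events classified by organ system and relatedness will be calculated for each group and compared" by Chi-square or Fisher's exact test. I read organ system and relatedness as two separate classifications. The general rule is two-sided testing at 5%, with .01 for secondary outcomes. The plan does not say which level applies to AEs.

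On masking, section 5 (Research Abstract) defines single-blind to mean that "examiners will not know participant treatment group assignment". Section 6 (Design and Randomization Plan) discloses the allocation to approved personnel other than the physical therapy testers. The masked role in section 6 (Assessments) is limited to outcome measures: "A trained research assistant (masked to the intervention assignment) will administer outcome measures at baseline, prior to randomization", with the same assessments repeated later.

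On AE capture, section 6 (Adverse Events) has events monitored "by all study staff who interact with the participant, including during on-site assessment visits, intervention sessions" and monthly calls. A causality judge, the site principal investigator, is named only for events between consent and randomization. After randomization all AEs are collected whatever their relation to study procedures. The Data and Safety Monitoring Board and its Safety Officer (section 8) are given no masked relatedness review.

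**The concern.** Randomization protects a comparison of what happened to participants. It does not protect a label attached afterwards by someone who may know the arm. The protocol itself sets different expectations for the two arms: section 8 names functional hip strengthening as a situation with a fall risk, and only the hip-focused group receives it (section 6, Interventions). A fall or a sore hip could be called related more readily in that group than the same event in the spine-focused group. The error can also run the other way and mask a true excess in the experimental arm. At stake is the reading of one published safety p-value. The efficacy analysis is not touched.

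**Working it through.** The plan states no AE rate, attribution rate or power for this comparison, so there is no figure to reproduce. The calculation below only shows how far the test can move if labelling differs.

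**Inputs from the documents.** 180 participants with equal allocation (section 6), so 90 per arm; no dropout is assumed. Two-sided 5% (section 10).

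**Assumed inputs.** The risk *r* of at least one AE is equal in both arms. A fraction *q* of participants with an AE has one called related, and *q* may differ by arm.

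**Formulas.** The probability of a related AE in arm *j* is π_j = r × q_j. The rejection probability is the sum, over all counts *a* and *b* from 0 to 90, of Bin(a; 90, π₁) × Bin(b; 90, π₂) for the pairs (a, b) that the test declares significant. Chi-square has no continuity correction: z = [(a − b)/90] / √[p̄(1 − p̄) × 2/90], with p̄ = (a + b)/180, rejecting at |z| ≥ 1.96.

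**Result at r = 40% in both arms, 5% level.**

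| Called related | Related AE by arm | Chi-square rejects | Fisher rejects |
|---|---|---|---|
| 50% vs 50% | 20% vs 20% | 5% | 3% |
| 50% vs 45% | 20% vs 18% | 6% | 4% |
| 50% vs 40% | 20% vs 16% | 10% | 8% |
| 50% vs 35% | 20% vs 14% | 18% | 14% |
| 50% vs 25% | 20% vs 10% | 47% | 40% |

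In every row the true difference in AE risk is zero.

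**Sensitivity.** At 50% vs 25%, letting *r* run from 30% to 50% moves the Chi-square figure from 36% to 58%. If the .01 level applies, the 50% vs 25% row at r = 40% becomes 23%/18%, against a nominal 1%.

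**Opposite direction.** With all-cause risks of 50% and 40%, attribution of 40% and 50% respectively gives 0.50 × 0.40 = 0.40 × 0.50 = 20% related in both arms. The true difference disappears from the related-AE comparison.

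**The alternative test.** Comparing any-cause AEs at 40% in both arms rejects 5.2% (Chi-square) or 3.7% (Fisher) of the time and uses no causality label.

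**The case against.** Four arguments have weight.

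- **Arm knowledge is inferred.** No section says who judges relatedness after randomization or whether that person is masked. AE reporting forms exist (section 6, Additional Participant Communication), and the data collection forms were filed separately (section 15), so criteria may be set there. Relation to study procedures also covers testing common to both arms. This stands. A reader might infer that the plan has unmasked staff judge causality, or that the arms have no common definition of related. The documents establish neither.
- **Other comparisons are planned.** Those by organ system and of individual events above 10% need no causality call. This also stands. A reader might infer that the safety conclusion as a whole is unsound, but nothing in the plan rests it on relatedness. Unmasked detection at treatment sessions could still affect these comparisons, and the fix would not remove that.
- **Relatedness can add information.** It can filter out background illness in people aged 60 to 85, so it would be wrong to say that it adds nothing but bias. As an assumed illustration, take an independent background risk of 40% and true treatment-caused AEs of 15% vs 5%. The all-cause risks are 1 − 0.60 × 0.85 = 49% and 1 − 0.60 × 0.95 = 43%. Chi-square/Fisher power is then 12%/9%, against 63%/55% for a correctly attributed comparison. This stands as a cost of the change. It presumes correct attribution, which the plan does nothing to secure.
- **The gap may be small.** Both arms have heat, manual therapy, trunk exercises and a home programme over 16 visits. A five- or ten-point gap has a modest effect, as the table shows. The documents cannot settle which gap is realistic.

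**Conclusion.** The concern holds for the relatedness comparison only. The plan attaches a p-value to a label whose post-randomization judge, criteria and masking are not stated, in a trial where only examiners are masked and one arm has a component that the protocol names as a fall risk. A significant difference in related AEs could therefore not be read as harm. The inflation is unknown: from almost none with a five-point attribution gap to roughly 40–47% rejection with a twofold gap, assuming 40% AE risk in both arms and 90 per arm. The conclusion rests on the probable, not documented, knowledge of the arm by whoever assigns the label. The change is worth making because an attribution-free comparison can be built from data already being collected.

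**What to change.** In section 10, Aim 1, AE paragraph:

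1. Add, as the leading safety comparison, the proportion of participants in each arm with at least one AE of any cause, and likewise with at least one serious AE.
2. Keep the organ-system comparisons, and state that they count participants rather than events.
3. Report relatedness by arm as counts and percentages without a p-value, with a note that it may have been judged with knowledge of the arm.

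The cost is a few sentences. All AEs after randomization are already collected regardless of relatedness, so no data, visits or staff are added. The loss is one test that could be more sensitive, since any-cause counts include unrelated illness and dilute a true difference. The descriptive table keeps the relatedness information in view.

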8. RISKS AND BENEFITS

List all potential physical, psychological, social, financial or legal risks to subjects (risks listed here should be included on the consent form).

Minimal risks to the subjects are expected. The risks of the physical therapy interventions might include muscular strain/soreness. A small risk of a fall (and concurrent injury) during functional performance testing or functional hip strengthening is present. As with any physical activity, there is the possibility that the participant's typical symptoms in the low back and/or hip might increase, although unlikely. There is also the potential for new musculoskeletal pain to occur secondary to physical activity. With increased or new symptoms, the treating therapist will modify the intervention. Study participants will be free to withdraw from participating in the study at any time if they are uncomfortable with any of the procedures. Although no other risks or changes in the existing minimal risks are anticipated, participants will be informed if any new information arises regarding risks of participation that may affect their decision to continue in the study.

In your opinion, are risks listed above minimal* or more than minimal? If more than minimal, please justify why risks are reasonable in relation to anticipated direct or future benefits.

We consider these risks to be minimal given that proposed functional performance tasks are similar to those performed in daily activities and commonly used during physical therapy evaluations, and that the interventions included in this clinical trial are those typically prescribed by physical therapists to reduce musculoskeletal complaints.

*(*Minimal risk means the probability and magnitude of harm or discomfort anticipated in the research are not greater than those ordinarily encountered in daily life or during the performance of routine physical or psychological examinations or tests)*

What steps will be taken to minimize risks?

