Statistical Analysis: [name] will supervise the data analyses for this proposal along with [name] and all analyses will be performed using SAS software, version 9.4 (SAS Institute, Inc., Cary, NC). The primary analyses will be done using intention-to-treat methods. We will compare the two groups on baseline characteristics to assess the adequacy of the randomization. Baseline characteristics include analgesic use, age, number of comorbidities, body mass index, gender, and race/ethnicity). If statistically or clinically significant between-group differences are noted, we will conduct sensitivity analyses controlling for the unbalanced variables to assess the impact on the inference for the treatment groups. Prior to conducting all of the statistical analyses outlined below, we will evaluate the assumptions of the statistical models and outliers and influential cases will be screened for and removed. All tests will be two sided with type I error of 5%. In order to reduce type I errors, secondary outcomes will be examined using an alpha = .01.

Aim 1: Primary Hypothesis. Following 8 weeks of treatment, a greater improvement in LBP-related disability and physical function (as measured by change in Quebec LBP Disability score and self-selected gait speed, respectively) will be observed for individuals that receive HIP+ compared to spine-focused rehabilitation (SFR).

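### Adverse events are compared between arms by Chi-square or Fisher's exact tests alone; with 90 per arm, a non-significant result for events at about 10% or below cannot exclude an important excess, so a risk difference with a 95% CI should be planned

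*Combined protocol and SAP*

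**What the plan says.** The harms analysis is one sentence in section 10 (DATA, Statistical Analysis), within the text for Aim 1. It covers "The rates of individual adverse events and serious adverse events that occur >10% and adverse events classified by organ system and relatedness", and these "will be calculated for each group and compared using Chi-square or Fisher's exact tests". So a rate per arm is a planned output, and the between-arm comparison is a significance test. The section mentions no risk difference, risk ratio or confidence interval for harms.

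No significance level is assigned to adverse events by name. The general rule in the same section is "All tests will be two sided with type I error of 5" percent, and "secondary outcomes will be examined using an alpha = .01". Section 6 (PROCEDURES) describes adverse events ("Adverse Events: The occurrence of AEs is monitored for each participant on an ongoing basis throughout the study by all study staff") after the Primary Outcome Measures heading and before the Secondary Outcome Measures heading, so 5% is the natural reading.

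On size, section 6 says "In total, 180 participants meeting the inclusion/exclusion criteria will be randomly assigned into one of two intervention groups", with a plan meant to ensure that "an equal number of participants are randomly assigned to each of the two treatment conditions".

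**The concern.** A significance test answers whether the data rule out equal rates. The more useful question about harms is how large an excess the data leave open. In a trial of this size the two can diverge: a test can be non-significant while the data remain compatible with a large excess. Conversely, when several event types and classes are each tested, an isolated p < .05 is not surprising.

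The matter is of practical interest here. Participants are 60 to 85 years old, and section 8 (RISKS AND BENEFITS) acknowledges that "A small risk of a fall (and concurrent injury) during functional performance testing or functional hip strengthening is present". Functional hip strengthening belongs to the hip-focused arm only. What is at stake is what a reader can conclude about harm from the final report: a statement that a difference was not significant, or the range of excess risk that was not excluded.

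**Working it through.** **Inputs from the documents.** 180 randomised in equal numbers, so 180/2 = 90 per arm; two-sided 5% from the general rule; Chi-square or Fisher's exact test; a 10% threshold for individual events.

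**Assumptions.** Event rates per arm, the number of tests and their independence, since the documents state none of these. Each event is counted as participants with at least one occurrence, which is what these tests require. The plan gives no power figure for harms, so there is none to reproduce.

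**1. Power for a doubling.** Normal approximation for 10% versus 20%:

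- SE under no difference = √(0.15 × 0.85 × 2/90) = 0.0532
- SE under the alternative = √(0.10 × 0.90/90 + 0.20 × 0.80/90) = 0.0527
- Power ≈ Φ((0.10 − 1.96 × 0.0532)/0.0527) = Φ(−0.08) ≈ 47%

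Exact enumeration of two binomials with n = 90 each, uncorrected Chi-square and Fisher:

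| True rates | Chi-square | Fisher |
|---|---|---|
| 5% vs 10% | 24% | 17% |
| 7% vs 14% | 34% | 27% |
| 10% vs 20% | 47% | 40% |
| 12% vs 24% | 56% | 49% |
| 15% vs 30% | 68% | 62% |
| 20% vs 40% | 84% | 80% |

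Power passes 50% at a lower-arm rate of about 11% (Chi-square) or just over 12% (Fisher). For 10% versus 20%, 80% power by the normal approximation would need 199 per arm.

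The 5% versus 10% row matters mainly for organ-system and relatedness classes. On a plain reading these are not subject to the 10% threshold, whereas an individual event at those rates would mostly not be tested.

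**2. What the test hides at 18/90 versus 9/90 (illustrative counts).**

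- Chi-square: (0.10/0.0532)² = 3.53, p = .060. Fisher: p = .094.
- Wilson 95% limits: 13.0% to 29.4% for 18/90, and 5.3% to 17.9% for 9/90.
- Newcombe lower limit: 0.10 − √((0.200 − 0.130)² + (0.179 − 0.100)²) ≈ −0.005
- Newcombe upper limit: 0.10 + √((0.294 − 0.200)² + (0.100 − 0.053)²) ≈ 0.205

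The 95% CI for the excess is −0.5 to +20.5 percentage points. The test is non-significant, but an excess of 20 points is not excluded.

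**3. Chance of at least one false positive, k independent tests.** 1 − (1 − size)^k:

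- At a true 5%: k = 10, 1 − 0.95^10 = 40%; k = 20, 1 − 0.95^20 = 64%.
- Fisher's actual size at a 10% rate is about 3.05%: k = 10, 1 − 0.9695^10 = 27%; k = 20, 1 − 0.9695^20 = 46%.

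**4. Sensitivity, 10% versus 20% (Chi-square/Fisher).** If the 1% level applied, power falls to 23%/18%, and the false-positive chance for 10 to 20 tests falls to 10% to 18%. With 77 per arm (an assumed loss of about 15%) at 5%, power is 42%/33%.

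**The case against.** Much of the case on the other side stands, and it limits the point.

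- **Common events.** A reader might infer that a doubling of any common adverse event would usually be missed. The table above does not support this: from 12% versus 24% by Chi-square, and slightly higher by Fisher, the doubling is detected more often than not.
- **Many false signals.** A reader might take 40% to 64% as the plan's error rate. The documents give no count of tests, and the 10% threshold limits individual-event tests. Individual events, organ systems and relatedness classes recount the same occurrences, so the independence formula is rough. Fisher's conservatism lowers the figure further.
- **Misreporting.** A reader might infer that p > .05 will be reported as equal safety, or a lone p < .05 as a harm signal. The documents say neither, and contain no equivalence or safety conclusion. They also contain no caution against such readings.
- **Nothing but p-values.** Rates per arm are planned, and a reader could derive an interval from them. A DSMB reviews safety twice a year (section 8). But DSMB review does not define the final between-arm analysis, and an interval that a reader could work out is not one the plan commits to report.
- **Falls.** The stated fall risk is small and attaches also to performance testing, which both arms undergo. Falls may never reach the 10% threshold, so this is context rather than evidence of an excess.
- **The remedy.** An unadjusted 95% CI has essentially the same precision and multiplicity as a 5% test. This is correct; the gain lies in showing the uncertainty.

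**Conclusion.** The point holds in limited form. The plan compares harms between arms by significance tests, with no difference or interval. For events at about 10% or below in the lower arm, a true doubling is missed more often than not (53% by Chi-square and 60% by Fisher at 10% versus 20%), so a non-significant result there says little about safety. For markedly more common events the tests perform adequately. The false-positive figures indicate order of magnitude only.

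This rests on 90 analysed per arm, the general 5% level applying to adverse events, and assumed event rates. It is a cheap improvement to the reporting of harms. It does not affect the efficacy analyses, and the documents do not support a claim that harms will be misreported.

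**What to change.** In the adverse event sentence of section 10 (Aim 1), make the planned between-arm comparison the risk difference with a 95% CI, for example a score-based interval, for each adverse event summary alongside the per-arm rates. Label these comparisons descriptive. If Chi-square or Fisher p-values are kept, call them supportive, state the level that applies, and add that p > .05 will not be read as equal safety.

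The cost is a sentence or two in the plan and a few lines of code in the SAS software already named. No new data are needed and trial conduct does not change. The interval adds no power and does not remove multiplicity. The small downside is that the report no longer gives a yes/no safety verdict.
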